5.2. OUTCOMES

5.2.1. Primary outcomes

The outcomes of interest for this study are urinary tract cancers, bladder cancer, and renal cancer. These outcomes will be identified through Clinical Practice Research Datalink's General Practitioner OnLine Data (CPRD-GOLD and CPRD Aurum) data in the UK, the Swedish cancer registry (SCR) in Sweden and Finnish cancer registry (FCR) in Finland.

Table 8 Main outcomes

[figure not shown]
Outcome	Definition	Details	Data source
Urinary tract cancer (malignant or carcinoma in situ)	First record of urinary tract cancer (ICD-10, ICD-O-3 and READ diagnosis codes in Annex I). During follow-up.	Time to first event during follow-up.	UK: CPRD-GOLD and Aurum Sweden: SCR Finland: FCR
Bladder cancer (malignant and carcinoma in situ)	First record of bladder cancer (ICD-10, ICD-O-3 and READ diagnosis codes in Annex I). During follow-up.	Time to first event during follow-up.	UK: CPRD-GOLD and Aurum Sweden: SCR Finland: FCR
Renal cancer (malignant)	First record of renal cancer (ICD-10, ICD-O-3 and READ diagnosis codes in Annex I). During follow-up.	Time to first event during follow-up.	UK: CPRD-GOLD and Aurum Sweden: SCR Finland: FCR

The date of diagnosis of the first incidence of urinary tract cancers as specified in CPRD-GOLD and CPRD Aurum, in the SCR or in the FCR after the entry into the study will be used as the primary outcome date.

[figure not shown]
In the Swedish and Finnish datasets, urinary tract cancer events will be identified from the SCR and FCR using ICD-10 and ICD-O-3 codes (Annex I).

In CPRD, urinary tract cancer events will be identified in CPRD-GOLD using READ codes and in CPRD Aurum using READ and SNOMED CT codes (Annex I).

Proprietary confidential information © 2024 Boehringer Ingelheim International GmbH or one or more of its affiliated companies

Proprietary confidential information © 2024 Boehringer Ingelheim International GmbH or one or more of its affiliated companies

5.3. COVARIATES

5.3.1. Demographics and other baseline variables

Table 11 Demographics and other baseline variables.

Variable	Definition	Details	Data source
Age at index	Patient age at index. Evaluated at index date.	Time-fixed Continuous Categorical: 18-49 50-64 65-69 70-74 75-79 80-84 85 and over	UK: CPRD Sweden: SPDR Finland: FPR, Population register centre
Sex	Patient sex. Evaluated at index date.	Time-fixed Categorical: Female Male	UK: CPRD Sweden: SPDR Finland: Population register centre
Highest level of education	Patient highest level of education Evaluated for the calendar year of the index date.	Time-fixed Categorical: Compulsory Upper secondary Post secondary	UK: N/A Sweden: Longitudinal integration database for health insurance and labor market studies (LISA) Finland: Statistics Finland

Proprietary confidential information © 2024 Boehringer Ingelheim International GmbH or one or more of its affiliated companies

Disposable income, individual at index	Patient available income. Evaluated for the calendar year of the index date.	Time-fixed Continuous Categorical: ¹ < Q1 ≥ Q1 – < Q2 ≥ Q2 – < Q3 ≥ Q3	UK: N/A Sweden: LISA Finland: N/A
Disposable income, family at index	Patient family income. Evaluated for the calendar year of the index date.	Time-fixed Continuous Categorical: ¹ < Q1 ≥ Q1 – < Q2 ≥ Q2 – < Q3 ≥ Q3	UK: N/A Sweden: LISA Finland: N/A
Socioeconomic summary variable	Socioeconomic status based on area of residence. Evaluated at index date.	Time-fixed Categorical: ¹	UK: CPRD Sweden: N/A Finland: N/A
CPRD database	Source of CPRD data Evaluated at index date.	Time-fixed Categorical: ¹ GOLD Aurum	UK: CPRD Sweden: N/A Finland: N/A
Calendar year of index date	Calendar year of index date. Evaluated at index date.	Time-fixed Categorical: ¹ 2014 2015 2016 2017 2018 2019 2020 2021	UK: CPRD Sweden: SPDR Finland: FPR

Proprietary confidential information © 2024 Boehringer Ingelheim International GmbH or one or more of its affiliated companies

Duration of look-back period (in years)	Time difference between index date and database membership start. Evaluated at index date.	Time-fixed Continuous Categorical: 1 2 – 5 6 – 9 10 and over	UK: CPRD Sweden: Total population register ² Finland: Population register centre
BMI	Patient BMI value at index. Evaluated at index date using closest value.	Time-fixed Continuous Categorical: <20 ≥20-24.9 25-29.9 >30	UK: CPRD Sweden: NDR Finland: AvoHILMO, EMR databases
Smoking status	Patient smoking status at index date. Evaluated at index date using closest value.	Time-fixed Categorical: Yes ³ No	UK: CPRD Sweden: NDR Finland: AvoHILMO, EMR databases
Alcohol use status	Patient alcohol use status at index date. Evaluated at index date using closest value.	Time-fixed Categorical: Yes No	UK: CPRD Sweden: NA Finland: NA
HbA1c value (in mmol/mol)	Time-dependent HbA1c measurement value in mmol/mol. Initialized at index using closest value to index date and updating from index date onwards.	Time-dependent Continuous Categorical: < 48 (6.5%) ≥48 (6.5 %)- <64 (8 %) ≥64 (8%)	UK: CPRD Sweden: NDR Finland: EMR databases

Proprietary confidential information © 2024 Boehringer Ingelheim International GmbH or one or more of its affiliated companies

Number of albuminuria tests	The number of albuminuria tests received by the patient prior to index date. Evaluate at index using all available history prior to index date.	Time-fixed Continuous	UK: CPRD Sweden: NDR Finland: EMR databases
-----------------------------	---	--------------------------	---

¹ The national patient register will be used if data on immigration/emigration are unavailable from the Total population register.

² Categories under-weight (<20), normal weight (20-24.9), overweight (25-29.9), and obese (>30) may be adjusted based on the observed distribution of the data.

³ In Sweden, a smoker is a patient smoking one or more cigarettes per day or a pipe daily or who had stopped smoking within the past 3 months. If data allows, categories current, never, past will be used.

5.3.2. Concomitant diseases

Table 12 Diabetic complications variables.

Variable	Definition	Details	Data source
Time since first diabetes diagnosis at index date	Time difference between [index date] and [first type 2 diabetes diagnosis date]. ICD-10 and READ diagnosis codes for type 2 diabetes in Annex I. Evaluated at index date.	Time-fixed Continuous Categorical: < Q1 ≥ Q1-< Q2 ≥ Q2-< Q3 ≥ Q4	UK: CPRD Sweden: NDR Finland: HILMO, AvoHILMO
Duration of treated diabetes at index date	Time difference between [index date] and [first antidiabetic treatment prescription/purchase date] in the data. ATC codes for antidiabetic treatment in Annex II. Evaluated at index date.	Time-fixed Continuous	UK: CPRD Sweden: SPDR Finland: FPR
Diabetic complications at index date	The variable is evaluated at index date and indicates the number of recorded diagnoses of diabetic complications using all available history prior to index date. ICD-10, READ diagnosis codes and corresponding NDR variables for diabetic complications in Annex I. Evaluate at index using all available history prior to index date.	Time-fixed Continous Categorical: 0 1-2 >2	UK: CPRD Sweden: NPR Finland: HILMO, AvoHILMO

Proprietary confidential information © 2024 Boehringer Ingelheim International GmbH or one or more of its affiliated companies

Diabetic retinopathy or diabetic maculopathy at index date	
The variable is evaluated at index date and indicates a register record with a diagnosis of diabetic retinopathy or diabetic maculopathy using all available history prior to index date.
 
ICD-10, READ diagnosis codes and corresponding NDR variables for diabetic retinopathy or diabetic maculopathy in Annex I.
 
Evaluated at index using all available history prior to index date.
	Time-fixed Categorical: Yes No	UK: CPRD Sweden: NPR NDR Finland: HILMO, AvoHILMO
Diabetic nephropathy at index date	
The variable is evaluated at index date and indicates a register record with a diagnosis of diabetic nephropathy using all available history prior to index date.
 
ICD-10 and READ diagnosis codes for diabetic nephropathy in Annex I.
 
Evaluated at index using all available history prior to index date.
	Time-fixed Categorical: Yes No	UK: CPRD Sweden: NPR Finland: HILMO, AvoHILMO
Diabetic neuropathy at index date	
The variable is evaluated at index date and indicates a register record with a diagnosis of diabetic neuropathy using all available history prior to index date.
 
ICD-10 and READ diagnosis codes for diabetic neuropathy in Annex I.
 
Evaluated at index using all available history prior to index date.
	Time-fixed Categorical: Yes No	UK: CPRD Sweden: NPR Finland: HILMO, AvoHILMO
Peripheral vascular disease at index date	
The variable is evaluated at index date and indicates a register record with a diagnosis of peripheral vascular disease using all available history prior to index date.
 
ICD-10 and READ diagnosis codes for peripheral vascular disease in Annex I.
 
Evaluated at index using all available history prior to index date.
	Time-fixed Categorical: Yes No	UK: CPRD Sweden: NPR Finland: HILMO, AvoHILMO

Proprietary confidential information © 2024 Boehringer Ingelheim International GmbH or one or more of its affiliated companies

Diabetic lower limb severe complications at index date	The variable is initialized at index date and indicates a register record with a diagnosis of diabetic lower limb severe complications using all available history prior to index date. ICD-10 and READ diagnosis codes for diabetic lower limb severe complications in Annex I.	Time-fixed Categorical: Yes	UK: CPRD Sweden: NPR Finland: HILMO, AvoHILMO
--	---	-----------------------------------	--

Evaluated at index using all available history prior to index date.

¹ Categories to be defined based on the observed distribution of the data.

Table 13 Other non-diabetic concomitant disease variables.

Variable	Definition	Details	Data source
Kidney or genitourinary stones	
The variable is initialized at index date and indicates a register record with a diagnosis of kidney or genitourinary stones using all available history. If no diagnosis prior to index date, it is time-updated to indicate any diagnosis of kidney or genitourinary stones after index date.
 
ICD-10 and READ diagnosis codes for kidney or genitourinary stones in Annex I.
 
Initialized at index and updating from index date onwards.
	
Time-dependent Categorical: Yes No
	
UK: CPRD Sweden: NPR Finland: HILMO, AvoHILMO

Estimated glomerular filtration rate (eGFR) at index date	
eGFR estimate derived from serum creatinine measurement using the CKD-Epi equation:
 $\text{eGFR (mL/min/1.73 m}^2\text{)} = 141 \times \min(\text{S}_{\text{cr}}/\text{K}, 1)^a \times \max(\text{S}_{\text{cr}}/\text{K}, 1)^{-1.209} \times 0.993^{\text{Age}} \times 1.018 \text{ [if female].}$ 
a = -0.329 (females) or -0.411 (males).
 
Evaluated at index using closest value to index date.
	
Time-fixed Continuous Categorical <15 (ml/min/1.73 m²) (kidney failure) 15-29 (ml/min/1.73 m²) (severely decreased) 30-44 (ml/min/1.73 m²) (Moderately to severely decreased) 45-59 (ml/min/1.73 m²) (Mildly to moderately decreased) 60-89 (ml/min/1.73 m²) (Mildly decreased) ≥90 (ml/min/1.73 m²) (Normal)
	
UK: CPRD Sweden: NDR Finland: EMR databases

Proprietary confidential information © 2024 Boehringer Ingelheim International GmbH or one or more of its affiliated companies

Renal impairment at index date	
The variable is evaluated at index date and indicates an eGFR < 60 (ml/min/1.73 m²) in all available history prior to index date.
 
Evaluated at index date using all available history prior to index date.
	
Time-fixed Categorical Yes No
	
UK: CPRD Sweden: NDR Finland: EMR databases

UTI or pyelonephritis	
The variable is initialized at index date and indicates a register record with a diagnosis of UTI or pyelonephritis using all available history. If no diagnosis prior to index date, it is time-updated to indicate any diagnosis of UTI or pyelonephritis after index date.
 
ICD-10 and READ diagnosis codes for UTI or pyelonephritis in Annex I.
 
Initialized at index and updating from index date onwards.
	
Time-dependent Categorical: Yes No
	
UK: CPRD Sweden: NPR Finland: HILMO, AvoHILMO

Liver disease at index date	
The variable is evaluated at index date and indicates a register record with a diagnosis of liver disease using all available history prior to index date.
 
ICD-10 and READ diagnosis codes for liver disease in Annex I.
 
Evaluated at index date using all available history prior to index date.
	
Time-fixed Categorical: Yes No
	
UK: CPRD Sweden: NPR Finland: HILMO, AvoHILMO

ICU admission at index date	
The variable is evaluated at index date and indicates a record of ICU admission in all available history prior to index date.
 
Evaluated at index date using all available history prior to index date.
	
Time-fixed Categorical: Yes No
	
UK: CPRD Sweden: NA Finland: HILMO, AvoHILMO

Pancreatitis at index date	
The variable is evaluated at index date and indicates a register record with a diagnosis of pancreatitis using all available history prior to index date.
 
ICD-10 and READ diagnosis codes for pancreatitis in Annex I.
 
Evaluated at index date using all available history prior to index date.
	
Time-fixed Categorical: Yes No
	
UK: CPRD Sweden: NPR Finland: HILMO, AvoHILMO

Proprietary confidential information © 2024 Boehringer Ingelheim International GmbH or one or more of its affiliated companies

Congestive heart failure at index date	The variable is evaluated at index date and indicates a register record with a diagnosis of congestive heart failure using all available history prior to index date. ICD-10 and READ diagnosis codes for congestive heart failure in Annex I.	Time-fixed Categorical: Yes No	UK: CPRD Sweden: NPR Finland: HILMO, AvoHILMO
Evaluated at index date using all available history prior to index date.			
Systolic blood pressure at index date	Systolic blood pressure measurement value in mm Hg at index date. Evaluated at index using closest value to index date.	Time-fixed Continuous Categorical ¹ : < 120 ≥120-<139 ≥140-<159 ≥160	UK: CPRD Sweden: NDR Finland: EMR databases
Evaluated at index using closest value to index date.			
Diastolic blood pressure at index date	Diastolic blood pressure measurement value in mm Hg at index date. Evaluated at index using closest value to index date.	Time-fixed Continuous Categorical ² : < 80 ≥80-89 ≥90-99 100 or higher	UK: CPRD Sweden: NDR Finland: EMR databases
Evaluated at index date using all available history prior to index date.			
Hypertension at index date	The variable is evaluated at index date and indicates a register record with a diagnosis of hypertension, or two records within 6 months (180 days) of systolic blood pressure ≥ 140 and diastolic blood pressure ≥ 90 using all available history prior to index date. ICD-10 and READ diagnosis codes for hypertension in Annex I.	Time-fixed Categorical: ² Yes No	UK: CPRD Sweden: NPR, NDR Finland: HILMO, AvoHILMO, EMR databases

Proprietary confidential information © 2024 Boehringer Ingelheim International GmbH or one or more of its affiliated companies

Stroke at index date	The variable is evaluated at index date and indicates a register record with a diagnosis of stroke using all available history prior to index date. ICD-10 and READ diagnosis codes for stroke in Annex 1.	Time-fixed Categorical: Yes No	UK: CPRD Sweden: NPR Finland: HILMO, AvoHILMO
Evaluated at index date using all available history prior to index date.			
Myocardial infarction at index date	The variable is evaluated at index date and indicates a register record with a diagnosis of myocardial infarction using all available history prior to index date. ICD-10 and READ diagnosis codes for myocardial infarction in Annex I.	Time-fixed Categorical: Yes No	UK: CPRD Sweden: NPR Finland: HILMO, AvoHILMO
Evaluated at index date using all available history prior to index date.			
Autoimmune disease at index date	The variable is evaluated at index date and indicates a register record with a diagnosis of autoimmune disease using all available history prior to index date. ICD-10 and READ diagnosis codes for autoimmune disease in Annex I.	Time-fixed Categorical: Yes No	UK: CPRD Sweden: NPR Finland: HILMO, AvoHILMO
Evaluated at index date using all available history prior to index date.			
COPD at index date	The variable is evaluated at index date and indicates a register record with a diagnosis of COPD using all available history prior to index date. ICD-10 and READ diagnosis codes for COPD in Annex I.	Time-fixed Categorical: Yes No	UK: CPRD Sweden: NPR Finland: HILMO, AvoHILMO
Evaluated at index date using all available history prior to index date.			

¹ Modification of Diet in Renal Disease (MDRD) study <http://clinchem.aaccjnl.org/content/53/4/766.long>

² http://www.heart.org/HEARTORG/Conditions/HighBloodPressure/AboutHighBloodPressure/Understanding-Blood-Pressure-Readings_UCM_301764_Article.jsp#

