8.4 DATA SOURCES

Prior to the development of the protocol for this study, a feasibility assessment of three databases in Europe (CPRD [GOLD and Aurum] and data with potential for linkage [HES (Outpatient and Admitted Patient Care), and ONS mortality statistics] in the UK and the national registers in Sweden and Finland) was performed with the aim to detail the minimum data requirements for the study and to assess, for each potential data source, the data quality, completeness of recorded information for urinary tract malignancies, and possibility of linkage with cancer registries, mortality registries and other data sources. The minimal data requirements for data sources which were assessed are listed in [Table 5](#).

Table 5

Minimum data requirements and data availability for the UK and the national registries in Sweden and Finland.

	The UK				Sweden					Finland						
	CPRD (GOLD and Aurum)	HES	Mortal ity		Patient	Prescri ption	Cancer	Cause of	Diabet es	HILM O	AvohI LMO	Special Reimb	Prescip tions	Cause of	Cancer s	EMR databa
Age	X	X	X	X	X	X	X	X	X	X	X	-	X	X	X	
Sex	X	X	X	X	X	X	X	X	X	X	X	-	X	X	X	
Medication	X	-		X ³	X	-	-	X ⁵	-	-	-	-	X	-	X	
DDD	X	-	-	X	X	-	-	-	-	-	-	-	X	-	-	
Purchase date	X ¹	-	-	X	X	-	-	-	-	-	-	-	X	-	-	
Diagnoses	X	X	-	X ⁴	-	X	-	X	X	X	X ⁷	X ⁹	-	X	-	
Date of diagnosis	X	X	-	X	-	X	-	-	X	X	X ⁸	-	-	X	-	
Time of death	-	-	X	-	-	X	X	-	-	-	-	-	-	X	X	
Cause of death	-	-	X	-	-	X	X	-	-	-	-	-	-	X	X	
Smoking	X	-	-	-	-	-	-	X	X ⁶	X ⁶	-	-	-	-	X	
BMI	X	-	-	-	-	-	-	X	X ⁶	X ⁶	-	-	-	-	X	
HbA1c	X	-	-	-	-	-	-	X	-	-	-	-	-	-	X	

X = available in the register, - = not available in the register

1 Prescription date; 2 Month and year; 3 Treatment given in hospitals (no full coverage); 4 No primary care data; 5 Only type of medication; 6 Partial availability based on applicable diagnosis codes; 7 Only chronic diseases included in the special reimbursement scheme; 8 Start and end dates of the special reimbursement; 9 In case a special reimbursement was included in the purchase

AvoHILMO=Register of primary health care visits, BMI=body mass index, CPRD=Clinical Practice Research Datalink, DDD=Defined daily dose, EMR=electronic medical record, HbA1c=Glycated haemoglobin A1c, HES=Hospital Episode Statistics (Outpatient data, and Admitted Patient Care data), HILMO=Care register for health care; UK =The United Kingdom

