Total population register ⁶	Statistics Sweden	1 st Jan 2013 – index date	1 st Jan 2013 – 31 st Dec 2020
Longitudinal integration database for health insurance and labor market studies (LISA) ⁶	Statistics Sweden	1 st Jan 2013 – index date	1 st Jan 2013 – 31 st Dec 2020
National diabetes register (NDR) ⁷	Centre of Registers, Region Västra Götaland	1 st Jan 2012 – index date	1 st Jan 2012 – 31 st Dec 2020
Finland			

Proprietary confidential information © 2024 Boehringer Ingelheim International GmbH or one or more of its affiliated companies

Finnish Prescription Register (FPR) ⁸	Social Insurance Institution (SII)	1 st Jan 1994 – index date	1 st Jan 1994 – 31 st Dec 2020
Finnish Registry for Reimbursed Medications ⁹	Social Insurance Institution (SII)	1 st Jan 1996 – index date	1 st Jan 1996 – 31 st Dec 2020
Care Register for Health Care (HILMO) ¹⁰	National Institute for Health and Welfare (THL)	1 st Jan 1996 – index date	1 st Jan 1996 – 31 st Dec 2020
Register of Primary Health Care Visits (AvoHILMO) ¹¹	National Institute for Health and Welfare (THL)	1 st Jan 2011 – index date	1 st Jan 2011 – 31 st Dec 2020
Finnish cancer registry (FCR) ¹²	Cancer Society of Finland	1 st Jan 1953 – index date	1 st Jan 1953 – 31 st Dec 2020
Finnish Cause of Death Register ⁵	Statistics Finland	Not applicable	1 st Jan 2014 – 31 st Dec 2020
Four regional EMR databases (Helsinki, Espoo, Vantaa, and Helsinki University Hospital [HUS] area) ⁶	Cities of Helsinki, Espoo, and Vantaa, and Helsinki University Hospital	1 st Jan 2013 – index date	1 st Jan 2013 – 31 st Dec 2020
Population register centre ⁶	Population register centre	1 st Jan 2013 – index date	1 st Jan 2013 – 31 st Dec 2020

¹ Data since the register was established in July 2005.

² Data since ICD-10 codes have been used (1997-).

³ Data since the register was established (2001-).

⁴ Data since the registry was established (1958-).

⁵ Data since the start of the study period (2014-). However, data will also be extracted since one year before the start of the study period (2013-), as in few cases observations of dispensed study drugs defining the population may occur after death.

⁶ Data since 1 year before the start of the study period (2013-).

⁷ Data since 2 years before the start of the study period (2012-).

⁸ Data since the register was established (1994-).

⁹ Data since the register was established (1996-).

¹⁰ Data since ICD-10 codes have been used (1996-).

¹¹ Data since the register was established (2011-).

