- If no T2DM diagnosis is present in NDR data, search for a diagnosis in NPR data (inpatient and outpatient records) using the relevant ICD-10 diagnosis codes listed in Annex I.
- If no T2DM diagnosis is present in NDR or NPR, search for a previous (before index date) prescription of metformin in SPDR data using the ATC codes listed in Annex II.

Finland

Patients with a diagnosis of T2DM will be identified in following steps:

- Search for a diagnosis of T2DM in the reimbursement register using ICD-10 diagnosis codes listed in Annex I.
- If no T2DM diagnosis is present in the reimbursement register, search for a main diagnosis in AvoHILMO data using relevant ICD-10 diagnosis codes listed in Annex I.
- If no T2DM diagnosis is found in the reimbursement register or in AvoHILMO, search for a previous (before index date) prescription of metformin using the ATC codes listed in Annex II.

Exclusion criteria

Table 3 Exclusion criteria.

Criteria	Definition	Data source
History of cancer prior to index date	
A registered diagnosis of any cancer (excluding non-melanoma skin cancer) (ICD-10, ICD-7, ICD-O-3 and READ diagnosis codes in Annex I)
 
All available medical history prior to index date inclusive.
	
UK: CPRD-GOLD and Aurum
 
Sweden: Swedish cancer registry (SCR)
 
Finland: Finnish cancer registry (FCR)

Diabetes diagnosis other than type 2	
A diagnosis of type 1 diabetes mellitus (T1DM) or other non-type 2 diabetes identified using the country-specific identification algorithms described below.
 
Relevant ICD-10 codes and READ diagnosis codes are provided in Annex I.
 
All available medical history prior to index date inclusive.
	
UK: CPRD-GOLD and Aurum
 
Sweden: NDR and NPR
 
Finland: Reimbursement registry

Proprietary confidential information © 2024 Boehringer Ingelheim International GmbH or one or more of its affiliated companies

SGLT-2 inhibitor or DPP-4 inhibitor use any time prior to index date	Any prescription of a SGLT-2 inhibitor drug (including empagliflozin) or a DPP-4 inhibitor drug, alone or in combination. (ATC codes in Annex II)	UK: CPRD-GOLD and Aurum Sweden: SPDR Finland: FPR
All available prescription history prior to index date exclusive.		

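### Swedish time since first diabetes diagnosis has a calendar-driven ceiling unless NDR holds an onset date, and diagnosis sources already extracted are not used to date it

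*SAP*

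**What the plan says.** SAP Section 5.3.2, Table 12, defines the covariate as "Time difference between [index date] and [first type 2 diabetes diagnosis date" and lists its sources as "UK: CPRD Sweden: NDR Finland: HILMO, AvoHILMO". It is evaluated at index, both continuously and in quartile categories.

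SAP Section 4.2.3, Table 1, gives the extraction windows. The footnote for NDR reads "Data since 2 years before the start of the study period (2012", for AvoHILMO "Data since the register was established (2011", for HILMO "Data since ICD-10 codes have been used (1996" and for the Finnish reimbursement register "Data since the register was established (1996". The same section says that, where history goes back more than a year, all of it will be used to classify diabetes-related covariates.

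SAP Section 4.2.4 identifies T2DM from more sources than Table 12 uses to date it. Sweden searches NDR, then NPR, then earlier metformin prescriptions. Finland's first step is "Search for a diagnosis of T2DM in the reimbursement register using ICD-10 diagnosis codes listed in Annex I", followed by AvoHILMO and then metformin. Protocol Table 5 says what dates the reimbursement register holds: "Start and end dates of the special reimbursement".

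A second covariate in Table 12, duration of treated diabetes, counts from the first antidiabetic prescription or purchase in SPDR (Sweden) or FPR (Finland).

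**The concern.** Protocol Section 8.1 names disease progression as a driver of channelling between the two drug groups. Time since diagnosis is a candidate for the propensity score (protocol Annex 6; SAP 6.5.1) and is in the balance check (SAP 6.6.2). It enters the base Cox model only if its standardised difference is 10% or more (SAP 6.7.2).

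If the first date a source can return is the start of its extract, every longer duration collapses to the same value. A standardised difference below 10% then says nothing about true duration above that value, and no adjustment is triggered. Separately, patients who enter the cohort through a source that Table 12 does not list may have no value at all.

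**Working it through.** **Does the documents' evidence give NDR an onset date?** The date-of-diagnosis row of protocol Table 5 has 15 entries for 15 named columns (3 UK, 5 Swedish, 7 Finnish). Read in order, the Swedish diabetes register has a dash. The alignment of this row can be checked: footnote mark 8, which concerns special reimbursement, falls under that column. SAP 4.2.4 mentions NDR variables only for the registered type of diabetes. On these documents, the earliest NDR record since 2012 is the only date on offer.

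**Ceiling.** Ceiling = index date − extraction start. Index dates run from 1 August 2014 to 31 December 2020 in Sweden and Finland.

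| Source | Extract starts | Ceiling at first index (years) | Ceiling at last index (years) | Listed for this covariate |
|---|---|---|---|---|
| NDR | Jan 2012 | 2.6 | 9.0 | yes (only Swedish source) |
| NPR inpatient | Jan 1997 | 17.6 | 24.0 | no |
| NPR outpatient | Jan 2001 | 13.6 | 20.0 | no |
| AvoHILMO | Jan 2011 | 3.6 | 10.0 | yes |
| HILMO | Jan 1996 | 18.6 | 25.0 | yes |
| Finnish reimbursement register | Jan 1996 | 18.6 | 25.0 | no |
| SPDR | Jul 2005 | 9.1 | 15.5 | no (treated duration) |
| FPR | Jan 1994 | 20.6 | 27.0 | no (treated duration) |

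For an index date of 30 June 2020, the last that leaves about six months before the Swedish study end, the NDR ceiling is 8.5 years.

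**Average Swedish ceiling.** The yearly Swedish counts in protocol Table 6 (2014 to 2020) add up to the printed totals:
- Empagliflozin: 0 + 629 + 2,181 + 4,811 + 8,738 + 10,169 + 5,806 = 32,334.
- DPP-4 inhibitors: 3,214 + 10,305 + 12,126 + 13,677 + 12,798 + 11,673 + 4,688 = 68,481.

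I assumed index dates at mid-October 2014, mid-year for 2015 to 2019, and end of March 2020. The yearly ceilings are then 2.79, 3.5, 4.5, 5.5, 6.5, 7.5 and 8.25 years.
- Mean ceiling: 219,440.5 / 32,334 = 6.8 years for empagliflozin; 384,241 / 68,481 = 5.6 years for DPP-4. The 1.2-year difference is calendar time only, before matching.
- Share with a ceiling under 5 years (index before 2017): 2,810 / 32,334 = 8.7% against 25,645 / 68,481 = 37.4%.

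**What is lost.** Recorded duration = min(true duration, ceiling), in the best case where a patient is registered as soon as the extract or the disease begins. In Sweden, true durations of 5, 10 and 20 years are all recorded as 2.8 in October 2014 and as 4.5 in mid-2016. In mid-2018 they become 5, 6.5 and 6.5. A true 1 year is recorded as 1 at every index date.

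**Undated patients.** A Swedish patient reaches the NPR step only when NDR holds no T2DM diagnosis. A Finnish patient accepted on the reimbursement record need not appear in HILMO or AvoHILMO. The documents give no counts for either group. SAP Section 9 would place them in a missing category, and considers dropping the variable if more than 50% are missing.

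**The case against.** Four points stand against a larger claim.

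- A reader might infer that the covariate cannot separate short from long diabetes. It can below the ceiling; only separation above it is lost.
- A reader might infer that Finland is blind before 2011, or that an earlier Finnish source is ignored. HILMO is listed and starts in 1996, the same year as the reimbursement register. The 2011 start binds only patients whose first coded contact is in AvoHILMO, and the documents do not give that share.
- Duration of treated diabetes already has a longer look-back than NDR or AvoHILMO and is itself a propensity-score and balance covariate. Most patients start second- or third-line treatment, so treated duration is informative. It misses the untreated years.
- Matching within 90 days of the index date (SAP 6.5.2) gives matched patients ceilings that differ by at most about 0.25 years (90 / 365.25). The 1.2-year difference between groups therefore describes the unmatched cohort. No effect on the hazard ratio follows from these figures.

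The Swedish ceiling also depends on NDR holding no onset date. The support for that is one dash in a table read from PDF, some of whose other rows are visibly misaligned, although this row is consistent with its footnotes.

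Finally, the top category printed as ≥ Q4 might be read as leaving a quarter of patients unclassified. The income variables in Table 11 end at ≥ Q3 and this covariate is also kept continuous, so it is a label slip.

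**Conclusion.** The point holds as a low-cost improvement to one of two overlapping covariates, not as a demonstrated bias. If NDR supplies no onset date, Swedish durations above 2.6 to 9.0 years, depending on index date, cannot be told apart, and balance on the recorded value is no evidence of balance above that level. In Finland the gain from the reimbursement register is coverage, not an earlier start.

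In both countries the SAP uses a source to decide that a patient has T2DM and then does not use it to date the disease. That sits poorly with its own commitment to use all available diabetes history. If NDR does hold an onset date, the Swedish ceiling disappears and what remains is the undated patients.

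**What to change.** In SAP Table 12:

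1. Name the NDR date field, and say whether it is a recorded onset date or the first registration in the extract.
2. Define first diagnosis date as the earliest across the diagnosis sources already extracted. Sweden: NDR and NPR. Finland: reimbursement start date, HILMO and AvoHILMO. NPR has no primary care data (protocol Table 5), so it will help only some Swedish patients.
3. Leave first dispensing to duration of treated diabetes; adding it here would largely duplicate that covariate.
4. State that patients identified through metformin alone may remain undated and fall under the Section 9 missing-data rule.
5. Editorial: change ≥ Q4 to ≥ Q3 in Tables 12 and 18.

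The cost is one derivation and a few words. Every source is already in SAP Table 1, so no new data are needed.
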